Attachment 4. Protocol JGDN Pharmacokinetic and Immunogenicity Sampling Schedule

Pharmacokinetic and Immunogenicity Sampling (Part A and Part B)

Sample Number	Cycle	Day	Sampling Time	Olaratumab PK ^a	Combination agents PK ^b	Immunogenicity ^c
1	1	1	Prior to olaratumab infusion	X		X
2		8	Within 5 min post olaratumab infusion	X		
3	2	1	Within 15 min prior to olaratumab infusion	X		X
4		1	Within 5 min post chemotherapy infusion	X	X	
5		8	Within 5 min post olaratumab infusion	X		
6	3 and then every other cycle	1	Within 15 min prior to olaratumab infusion	X		X
7	30-day follow-up (Visit 801)	Any time		X		X

Abbreviation: PK = pharmacokinetics.

a A 2.5-mL (~1 mL if patient has <19kg) blood sample will be collected (to generate serum for bioanalysis).

b A 2-mL (~1 mL if patient has <19kg) blood sample will be collected (to generate plasma for bioanalysis).

c A 3.5-mL blood sample will be collected (to generate serum for anti-olaratumab antibody analysis).

Pharmacokinetic and Immunogenicity Sampling (Part C)

Sample Number	Cycle	Day	Sampling Time	Olaratumab PK^a	Combination agents PK^b	Immunogenicity^c
1	1	1	Prior to olaratumab infusion	X		X
2		1	Within 5 min post chemotherapy infusion	X	X	
3		8	Within 5 min post olaratumab infusion	X		
4	2	1	Within 15 min prior to olaratumab infusion	X		X
5		8	Within 5 min post olaratumab infusion	X		
6	3 and then every other cycle	1	Within 15 min prior to olaratumab infusion	X		X
7	30-day follow-up (Visit 801)		Any time	X		X

Abbreviation: PK = pharmacokinetics.

a A 2.5-mL (~1 mL if patient has <19kg) blood sample will be collected (to generate serum for bioanalysis).

b A 2-mL (~1 mL if patient has <19kg) blood sample will be collected (to generate plasma for bioanalysis).

c A 3.5-mL blood sample will be collected (to generate serum for anti-olaratumab antibody analysis).

### 3. Revision History

Statistical Analysis Plan Version	Approval Date	Notes
1	28-Apr-2016 GMT	Approval was prior to the first patient visit.
2	21-Nov- 2016 GMT	Version 2 was approved after protocol amendment a. Updates include updates to annual report analyses as well as clarification of sections text such as PK, interim, and study plan figure etc.
3	26-Nov- 2018 GMT	Version 3 includes updates related to the addition of Part C and Infusion Related Reaction definition update.

## 4. Study Objectives

### 4.1. Primary Objective

The primary objective of this study is to determine a recommended dose of olaratumab in combination with at least one of the studied chemotherapy regimens in pediatric patients based on any dose-limiting toxicities (DLTs) as well as olaratumab serum exposure-matching between the adult and pediatric populations.

### 4.2. Secondary Objectives

The secondary objectives of this study are:

- to investigate the pharmacokinetic (PK) of olaratumab as monotherapy and in combination with either doxorubicin, vincristine/irinotecan, or high-dose ifosfamide in pediatric patients;
- to assess immunogenicity in pediatric patients;
- to document any antitumor activity observed with olaratumab in combination with either doxorubicin, vincristine/irinotecan, or high-dose ifosfamide in pediatric patients.

### 4.3. Exploratory Objectives

- to identify exploratory biomarkers associated with tumor response and/or safety.

## 5. A Priori Statistical Methods

### 5.1. Study Design and Sample Size Consideration

Study I5B-MC-JGDN (JGDN) is a multicenter, dose-escalation, open-label Phase 1 pediatric safety clinical trial with 3 distinct components, Part A, B and C.

Part A will consist of at least 12 evaluable pediatric patients. Given the expected diversity of age and body weight in the study population, this sample size is expected to provide the necessary amount of PK information in order to characterize the disposition of olaratumab in the pediatric population. During Cycle 1 monotherapy, if the DLT rate is  $>1/3$  (for example, greater than 4 out of 12 patients), then the dose of olaratumab will be reduced to 10 mg/kg. If the DLT rate is  $>1/3$  in the first cycle (Cycle 2) of any of the combination therapy arms, then appropriate dose de-escalation of olaratumab for that combination will occur. Another cohort with at least 3 patients will be studied for that combination with olaratumab at 10 mg/kg.

Part B will be initiated after the following criteria have been met:

- Acceptable safety results, which must include a minimum of 6 evaluable patients, and the PK profile from Part A monotherapy.
- At least one of the 15 mg/kg combination arms has met the following DLT criteria: less than one-third (that is, approximately  $\sim 33.3\%$  [minimum of 3 patients]) DLT rate. Only the combination arms in Part A that have met these criteria may be studied in Part B.

Part B will consist of at least 12 evaluable pediatric patients. These patients will be treated for 1 cycle (21 days) of olaratumab monotherapy at 20 mg/kg on Day 1 and Day 8. If the patient does not experience a DLT in the first cycle of monotherapy, or meet any other criteria for discontinuation, the patient will then receive olaratumab (20 mg/kg) in combination with any of the 3 chemotherapy regimens in Part A that have successfully passed the DLT criteria described above for Part A (doxorubicin or vincristine/irinotecan or high-dose ifosfamide per investigator discretion). During Cycle 1 monotherapy, if the DLT rate is  $>1/3$  (for example, greater than 4 out of 12 patients), then the dose of olaratumab will be reduced to 15 mg/kg for patients subsequently enrolled. If the DLT rate is  $>1/3$  in any of combination therapy arms, then appropriate dose de-escalation of olaratumab for that combination will occur.

Part C patients will receive olaratumab (20 mg/kg) in combination with any of the 3 chemotherapy regimens (per investigator discretion) from Cycle 1 onward (i.e no olaratumab monotherapy in Cycle 1 of Part C). Parts B and C together will enroll up to 45 patients (approximately 15 per chemotherapy arm). Treatment will continue until disease progression or other discontinuation criteria are met. The planned duration of treatment is not fixed; patients will remain on study until they fulfill one of the criteria for study discontinuation as specified in the protocol.

This study will enroll a minimum of 24 (maximum of 79) pediatric patients, including a minimum of approximately 10 osteosarcoma patients and 10 rhabdomyosarcoma patients across all treatment arms, if possible. The goal will be to enroll approximately 20 evaluable patients in

each combination arm across Parts A, B and C to characterize the safety and PK profile of olaratumab and the respective chemotherapeutic agents, and to inform dose choice for potential later-phase studies.

Figure JGDN.1 provides an illustration of the study design (Part A, B and Part C). Figure JGDN.2 provides an Olaratumab dosing plan for Part A, B and Part C of the study.

Figure JGDN.1 Illustration of study design

[figure not shown]

Figure JGDN.2 Illustration of Olartumab Dosing Plan b						
Part A Cycle 1		Combination Cycle 2 a		Combination Cycle 3 a onward		Initiate Part B if:
15 mg/kg (~12 pts)	Acceptable DLT level	15 mg/kg	Acceptable DLT level	15mg/kg		Acceptable safety results, which must include a minimum of 6 evaluable patients, and the PK profile from Part A monotherapy
> 1/3 DLT			> 1/3 DLT Of any combination arm	10mg/kg (at least 3 pts)	No part B	At least one of the 15 mg/kg combination arms has met the following DLT criteria: less than one-third (that is, approximately ~33.3% [minimum of 3 patients]) DLT rate
10 mg/kg (~12 pts)		10mg/kg		10mg/kg	No part B	
Part B Cycle 1*		Part B - Combination Cycle 2 a / Part C Cycle 1 a		Part B - Combination Cycle 3 a onward / Part C – Combination Cycle 2 a onward		
20 mg/kg (~12 pts)	Acceptable DLT level	20 mg/kg	Acceptable DLT level	20 mg/kg		
> 1/3 DLT			> 1/3 DLT	15mg/kg		
15 mg/kg (~12 pts)	Acceptable DLT level	15 mg/kg	Acceptable DLT level	15 mg/kg		
> 1/3 DLT		> 1/3 DLT		10mg/kg		
		10mg/kg	Acceptable DLT level	10mg/kg		
		> 1/3 DLT	Study stop/reassess			
10 mg/kg (~12 pts)	Acceptable DLT level	10 mg/kg	Acceptable DLT level	10 mg/kg		
> 1/3 DLT (i.e. >4 of 12)		> 1/3 DLT				
Study stop/ reassess		Study stop or reassess				
a. In combination with any of the 3 chemotherapy regimens in Part A that have successfully passed the DLT criteria described above for Part A (doxorubicin or vincristine/irinotecan or high-dose ifosfamide per investigator discretion). b. Part A and B includes monotherapy treatment of Olaratumab in cycle 1 with the remainder being combination treatment. Part C includes combination treatment starting from Cycle 1.						

## 5.2. General Considerations

Statistical analysis of this study will be the responsibility of Eli Lilly and Company (Lilly). The analyses for this study will be descriptive, except for possible exploratory analysis as deemed appropriate. Data analyses will be provided by dose groups and for all study patients combined wherever appropriate. For continuous variables, summary statistics will include number of patients, mean, median, standard deviation, minimum, and maximum. Categorical endpoints will be summarized using number of patients, frequency, and percentages. Unless otherwise specified, missing data will not be imputed.

The interpretation of the study results will be the responsibility of the investigator with the Lilly Clinical Research Physician (CRP)/Clinical Research Scientist (CRS), pharmacokineticist, and statistician. The CRP or CRS and statistician will also be responsible for the appropriate conduct of an internal review for both the final study report and any study-related material to be authorized by Lilly for publication.

Exploratory analyses of the data not described below will be conducted as deemed appropriate.

## 5.3. Definitions of Analysis Variables

Definitions of safety and efficacy analysis variables are listed in Section 5.3.1 and Section 5.3.2, respectively.

The general analysis variables are listed below alphabetically.

- **Age (years):** (Informed Consent Date - Date of Birth + 1)/365.25.

Note. Average days in a year = 365.25, reflecting the Julian Year of 3 years with 365 days each and 1 leap year of 366 days. Birth month and day are imputed to be 01 July because only birth year is collected through the case report form (CRF).

- **Baseline measurement:** The last non-missing measurement prior to or on the first dose date will serve as the baseline measurement.
- **Duration is calculated as:**
  - Duration (days): (End Date - Start Date + 1)
  - Duration (weeks): (End Date - Start Date + 1)/7
  - Duration (months): (End Date - Start Date + 1)/30.4375
  - Duration (years): (End Date - Start Date + 1)/365.25
- **Study Day:** Study day indicates the number of days relative to the date of first dose. The day is calculated as assessment date - first dose date + 1 day if the assessment is done on or after the first dose day. If the assessment is done prior to the first dose day, study day will be calculated as assessment date - first dose date. Date of first dose is defined as Study Day 1.

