RECIST v1.1, RANO, or Macdonald Tumor Assessments	X			
Other Assessments				
Biomarker Sampling		X		
Biopsy/Tumor Tissue Submission	X			Optional sample from archived or new tumor tissue

Abbreviations: BSA = body surface area; C1D1 = Cycle 1 Day 1; CNS = central nervous system; CT = computed tomography; ECG = electrocardiogram; ECHO = echocardiogram; HCG = human chorionic gonadotropin; MRI = magnetic resonance imaging; MUGA = multigated acquisition; RANO = Response Assessment in Neuro-Oncology; RECIST v1.1 = Response Evaluation Criteria In Solid Tumors Version 1.1.

JGDN Study Schedule, Treatment Period for Olaratumab in Combination with Doxorubicin (Parts A and B)

All evaluations must be done on the day of study drug administration. In case of dose interruption, these evaluations will also be done at minimum frequency every 21 days (± 3 days).

Day	Treatment Period 21-Day Cycles						Comments	
	Cycle 1		Cycle 2-n					
	Day 1 (± 3)	Day 8 (± 3)	Day 1 (± 3)	Day 2 (± 3)	Day 8 (± 3)	Day 15 (± 3)		
Eligibility Assessments								
Lansky/Karnofsky performance status	X		X					
ECG	X		X				Consecutive replicate ECGs will be obtained (3 readings), whenever feasible for the patient, at approximately 1-minute intervals.	
ECHO or MUGA			X				ECHO or MUGA scans must be performed at the end of Cycles 2, 4, and 6 and when clinically indicated. Additional ECHO/MUGA may be performed at the investigator's discretion.	
Safety Assessments								
Physical Exam	X	X	X		X		Physical exam includes weight and BSA measurement.	
Vital Signs	X	X	X	X	X		Vital sign measurements include temperature, pulse rate, and blood pressure. Cycle 1: Obtain vital signs prior to and after the completion of the olaratumab infusion. In Cycle 2 and later: On Day 1, obtain vital signs prior to and after the completion of the olaratumab infusion (prior to dexamethasone, if used; or if not used, then prior to doxorubicin) and within 1 hour after completion of the doxorubicin infusion. On Day 2, obtain vital signs prior to dexamethasone infusion (patients receiving dexamethasone and doxorubicin) or prior to doxorubicin infusion (patients receiving doxorubicin only) and within 1 hour after completion of the doxorubicin infusion. On Day 8, obtain vital signs prior to and after the completion of the olaratumab infusion.	

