Lansky/Karnofsky performance status	X					
ECG	X				Baseline ECG can be used for C1D1 if completed within 7 days. Consecutive replicate ECGs will be obtained (3 readings), whenever feasible for the patient, at approximately 1-minute intervals.	
ECHO or MUGA	X				ECHO or MUGA scans must be performed PRIOR to Cycles 1, 3, and 5 and results must be available prior to doxorubicin administration for those cycles. Additional ECHO/MUGA may be performed at the investigator's discretion as clinically indicated.	
Safety Assessments						
Physical Exam	X		X		Physical exam includes weight and BSA measurement.	
Vital Signs	X	X	X		Vital sign measurements include temperature, pulse rate, and blood pressure. On Day 1, obtain vital signs prior to and after the completion of the olaratumab infusion (prior to dexamethasone, if used; or if not used, then prior to doxorubicin) and within 1 hour after completion of the doxorubicin infusion. On Day 2, obtain vital signs prior to dexamethasone infusion (patients receiving dexamethasone and doxorubicin) or prior to doxorubicin infusion (patients receiving doxorubicin only) and within 1 hour after completion of the doxorubicin infusion. On Day 8, obtain vital signs prior to and after the completion of the olaratumab infusion.	
Adverse Event Assessment	X	X	X		All AEs considered at least possibly related to study treatment will be followed until resolution, stabilization, return to baseline, or until deemed irreversible.	
Concomitant Medication Assessment	X	X	X			
Laboratory Assessments (See Attachment 2 for details)						
Hematology Profile	X		X	X	Hematology measurements must be collected on Day 15 only during Cycle 1 and Cycle 2.	
Coagulation Profile	X				Perform every other cycle beginning at Cycle 1 Day 1. Baseline value can be used for C1D1 if completed within 7 days.	
Chemistry Profile	X					
Urinalysis	X				Includes a routine urinalysis, and if clinically indicated, a microscopic analysis. If routine	

Day	Treatment Period 21-Day Cycles				Comments	
	Cycle 1-n					
	Day 1 ^a	Day 2 ^a	Day 8 ^a	Day 15 ^a		
					analysis indicates > 2+ proteinuria, then a 24-hour urine must be collected and must demonstrate ≤ 1000 mg of protein in 24 hours or urine protein/creatinine ratio < 1 , prior to proceeding to the next cycle.	

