Safety Assessments									
Physical Exam	X					X		Physical exam includes weight and BSA measurement.	
Vital Signs	X	X	X	X	X	X		Vital sign measurements include temperature, pulse rate, and blood pressure. On Day 1, obtain vital signs prior to and after the completion of the olaratumab infusion (prior to vincristine) and within 1 hour after completion of the irinotecan infusion. On Days 2-5, obtain vital signs prior to irinotecan infusion and within 1 hour after completion of the infusion. On Day 8, obtain vital signs prior to and after the completion of the olaratumab infusion (prior to vincristine) and within 1 hour after completion of the vincristine infusion.	
Adverse Event Assessment	X	X	X	X	X	X		All AEs considered at least possibly related to study treatment will be followed until resolution, stabilization, return to baseline, or until deemed irreversible.	
Concomitant Medication Assessment	X	X	X	X	X	X			
Laboratory Assessments (See Attachment 2 for details)									
Hematology Profile	X					X	X	Hematology measurements must be collected on Day 15 only during Cycle 1 and Cycle 2.	
Coagulation Profile	X							Perform every other cycle beginning at Cycle 1 Day 1. Baseline value can be used for C1D1 if completed within 7 days.	
Chemistry Profile	X								

Day	Treatment Period 21-Day Cycles							Comments	
	Cycle 1-n								
	Day 1 ^a	Day 2 ^a	Day 3 ^a	Day 4 ^a	Day 5 ^a	Day 8 ^a	Day 15 ^a		
Urinalysis	X							Includes a routine urinalysis, and if clinically indicated, a microscopic analysis. If routine analysis indicates > 2+ proteinuria, then a 24-hour urine must be collected and must demonstrate ≤ 1000 mg of protein in 24 hours, or urine protein/creatinine ratio < 1 , prior to proceeding to the next cycle.	
Pregnancy Test	X							Urine pregnancy test on Day 1 of every cycle or per local practice (whichever is of shorter duration) and at short-term follow-up visit. If the urine pregnancy test performed on Day 1 of the cycle is positive, confirm with a serum pregnancy test.	
Immunogenicity	See Attachment 4 for specific time points.							When possible, an immunogenicity sample will be collected at the same time as the PK sample. If a patient experiences an IRR to olaratumab, blood samples for immunogenicity and PK analysis will be taken at the following time points: (1) as soon as possible after the onset of the IRR, (2) at the resolution of the IRR, and (3) 30 days after the IRR.	
Efficacy Assessments									

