### **5.9.4. Vital Signs, Physical Findings, and Other Observations Related to Safety**

Actual value and change from baseline for vital sign measurements will be summarized at each assessment time point using summary statistics. Electrocardiogram, Echocardiogram(ECHO)/MUGA measurements will also be summarized at each assessment time point using summary statistics. Listings of vital signs, ECG, ECHO/MUGA and data will be provided.

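### The SAP's baseline rule has no pre-dose condition, so change from baseline in vital signs is measured from a post-dose Day 1 reading

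*SAP*

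**What the plan says.** SAP 5.3 gives one baseline definition for all measurements: "The last non-missing measurement prior to or on the first dose date will serve as the baseline measurement". The same section adds "Date of first dose is defined as Study Day 1". Neither sentence mentions time of day or requires the value to precede dosing, and the SAP has no separate definition for vital signs.

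In the study schedules (Protocol Attachment 1), Parts A and B carry the instruction "Cycle 1: Obtain vital signs prior to and after the completion of the olaratumab infusion" in all three chemotherapy arms, under the general requirement "All evaluations must be done on the day of study drug administration". Part C starts combination treatment in Cycle 1. Its schedules say "On Day 1, obtain vital signs prior to and after the completion of the olaratumab infusion" and add a third reading on the same date: "within 1 hour after completion of the doxorubicin infusion" in the doxorubicin arm, "within 1 hour after completion of the irinotecan infusion" in the vincristine/irinotecan arm, and a matching reading after ifosfamide in the third arm.

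SAP 5.9.4 then plans the output: "Actual value and change from baseline for vital sign measurements will be summarized at each assessment time point using summary statistics". Listings of vital signs are also planned.

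**The concern.** A baseline should describe the patient before treatment. Here the rule works by date, and the first dose date carries both untreated and treated readings, of which the last is always scheduled after dosing. The planned change tables would then use a treated value as the reference, at the one visit where the acute effect of a first infusion is measured directly. The protocol (Section 7.2.1) notes that Grade 3/4 infusion-related reactions have so far been seen only in Cycle 1, so a reader would look to these tables for the blood pressure, pulse and temperature response to the first infusion.

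The rule also sits badly with other parts of the documents. Protocol Table JGDN.8.1 closes the baseline period just before the first dose, and SAP 5.9.3 opens the postbaseline window for laboratory grading at the first dose. A Day 1 post-infusion reading is a baseline value under SAP 5.3 but would count as on-treatment under either of these.

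**Working it through.** The plan states no figure that depends on this rule, so there is nothing to reproduce. The check applies the rule to the scheduled readings.

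**Inputs**
- Baseline rule: last non-missing value up to and including the first dose date (SAP 5.3).
- Readings on that date, Parts A and B: two, before and after olaratumab (Protocol Attachment 1).
- Readings on that date, Part C: three, before olaratumab, after olaratumab and after chemotherapy (Protocol Attachment 1).
- Output: change from baseline at each time point (SAP 5.9.4).

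**Notation.** P is the pre-infusion value, d the change from before to after olaratumab, c the further change from after olaratumab to after chemotherapy (Part C), and e the true difference from P at a later visit.

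**Baseline as written.** It is P + d in Parts A and B, and P + d + c in Part C. Reported change is the reading minus that baseline:

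| Reading | Parts A/B, as written | Part C, as written | With baseline P |
|---|---|---|---|
| Day 1, before olaratumab | −d | −(d + c) | 0 |
| Day 1, after olaratumab | 0 | −c | d |
| Day 1, after chemotherapy | not taken | 0 | d + c |
| Later visit, value P + e | e − d | e − d − c | e |

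Every reported change is therefore off by −d in Parts A and B, and by −(d + c) in Part C.

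**Illustration, Parts A and B.** The documents give no expected vital-sign change, so the size is an assumption. For a first-infusion systolic fall of 5, 10 or 20 mmHg (d = −5, −10, −20), the Day 1 post-infusion change is reported as 0 in each case instead of −5, −10 or −20. A later visit back at P (e = 0) is reported as 0 − d = +5, +10 or +20, although nothing has risen above the untreated level.

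**Illustration, Part C.** Take d = −10 and let the patient recover by c = 0, 5 or 10 mmHg before the post-chemotherapy reading. The reported post-olaratumab change is −c = 0, −5 or −10, against a true −10. A later visit at P is reported as −(d + c) = +10, +5 or 0. The Part C error disappears only if the value has fully returned to P by the last Day 1 reading.

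**Mixed baselines.** Because the rule takes the last non-missing value, a patient whose post-dose Day 1 reading is missing falls back to an earlier one. Some patients could then have a pre-dose baseline and others a post-dose one. Parts B and C also take their baselines at different points on Day 1, although both are planned at 20 mg/kg.

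**The case against.** The strongest reply is that little is lost. SAP 5.9.4 reports actual values as well as changes, plus listings, so the pre- and post-infusion values can be compared whatever baseline is used. In Parts A and B the pre-infusion row of the change table would even show the effect with its sign reversed. This stands. The data survive, and what fails is the planned change summary.

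A reader might infer that the rule hides infusion-related reactions or weakens the safety decisions. The documents do not support that. SAP 5.3.1 finds these reactions from adverse-event terms with medical review, and it counts events on the day of infusion as immediate reactions. Dose-limiting toxicities are also defined from adverse events, and clinically significant vital-sign findings must be reported as adverse events (Protocol 8.1.2). No dose decision depends on a change from baseline in vital signs.

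A reader might also extend the point to ECG and laboratory values. That extension is weak. SAP 5.9.4 plans change from baseline only for vital signs, and the schedules show no separate post-infusion ECG. Laboratory shift tables do use a baseline (SAP 5.9.3), but only one Day 1 sample is scheduled, and the start-of-cycle criteria in Protocol 7.2.4 need the main haematology and liver results before dosing.

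Nor is the first post-infusion change zero in every part. In Part C it is −c, and only the post-chemotherapy change is zero by construction.

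Two defences of the text do not hold. The Part C footnote placing assessments before treatment cannot govern readings that the same schedule orders after infusion. And if programmers would choose the pre-dose value anyway, the SAP should say so.

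**Conclusion.** The point holds for the vital-sign change-from-baseline summaries and goes no further. Under the rule as written, every patient with a recorded post-dose reading on Cycle 1 Day 1 gets a treated baseline; with the planned maximum enrolment that is up to 79 patients. The zero change at the last Day 1 reading follows from the definition, not from an assumption about the drug. The size of the shift at other time points equals the net acute change by that last reading, which the documents do not give; the mmHg figures are illustrations only.

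This rests on two assumptions: that the rule is programmed literally, and that the scheduled post-dose readings are recorded. In a descriptive study with actual values also tabulated, the consequence is a set of misleading tables, not a wrong dose recommendation. It is still worth correcting, because the rule is explicit and its result is wrong.

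**What to change.** In SAP 5.3, define baseline as the last non-missing measurement taken before the start of the first infusion of any study drug, judged by date and time. Where the time is missing, use the reading scheduled as pre-dose on Day 1. In SAP 5.9.4, label the Day 1 pre-infusion, post-olaratumab and (Part C) post-chemotherapy readings as separate time points, so that the Day 1 changes become d and d + c as in the last column of the table.

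The cost is one SAP sentence and a programming condition. No new data are needed, because Protocol 8.4 already requires the actual collection time on the eCRF.

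One limit remains. Premedication is given 30 to 60 minutes before olaratumab (Protocol 7.2.1), and the schedule does not place the pre-infusion reading before it. The revised baseline is therefore free of study drug but may still carry a premedication effect.
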